- If the patient was already receiving RRT, indicate whether it was discontinued in the past 24 hours by checking appropriate “Yes/No” box on line 16. If the patient was not previously receiving RRT, check the N/A box.
- On line 17, please if indicate if any of the adverse events occurred in the last 24 hours by checking the appropriate “Yes/No” boxes.
- Enter the lowest and highest values since randomization from the EMR for systolic and diastolic blood pressure and mean arterial pressure in mm Hg in the appropriate fields on line 15. Record the lowest and highest values for CVP in cm H2O. If no CVP measurements check the “CVP not available” box. If only one measurement for any of the vital signs, enter the value in the “Lowest” CVP box and check the “Single” box.
- In the table on line 19 enter for each 2-hour period in the previous 24 hours the highest and lowest recorded core temperatures, check the box next to the location of the probe, and enter the lowest recorded SpO2 value, the corresponding FiO2, and the most concurrently measured Mean Airway Pressure. If there is only a single temperature measurement during the period, record in the “Lowest” field and check the “Single value” box. If there are no SpO2 measurements during a 2-hour period, indicate by checking the “None” Box for SpO2. If the patient was receiving supplemental oxygen by NC, calculate the FiO2 using the formula:  $FiO_2 = 0.21 + 0.03 \times \text{flow rate in LPM}$ .
- Indicate whether the patient received corticosteroids in the last 24 hours by checking the appropriate “Yes/No” box on line 20. If “Yes,” enter the total dose in hydrocortisone equivalents using the conversion, 1 mg prednisone or methylprednisolone = 4 mg hydrocortisone and 1 mg dexamethasone = 25 mg hydrocortisone.
- Indicate whether the patient received an inhaled vasodilator in the last 24 hours by checking the appropriate “Yes/No” box on line 21. If “Yes,” indicate which agent by checking the appropriate box and recording the total number of hours the at least one agent was administered.
- Indicate if the patient received vasopressor support at any time since randomization by checking the appropriate “Yes/No” box on line 22. If “Yes,” check the box next to each of the agents that was received, the highest infusion rate (and units) received, and the total hours receiving any vasopressor support. If “No” skip to question 23.

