- On line 23, indicate whether a proning protocol was started or stopped in the preceding 24 hours.
- Beginning on line 24, record the lowest and highest values for each indicated laboratory value since randomization. If there is only one value, record it in the lowest value field, and click the “Single” box. If there are no data, check the “None” box.
- In the appropriate fields in table beginning on line 25, enter the lowest and highest blood glucose values (from finger sticks) and the date and time of the measurements for each 6-

hour period since randomization. If there is only a single value, record in the “Lowest Glucose” field and check the “Single Value” box for that 6-hour time period. If there are no glucose measurements, click the “None” box for that 6-hour time period.

- If the patient was extubated prior to Study Day 2 (or 3) skip to question 34.
- If intubated and receiving mechanical ventilation for any part of day 2 (or 3) indicate all ventilator modes used in the last 24 hours by checking the appropriate boxes under line 26 and circle the mode used at 0800.
- Indicate whether the patient was extubated in the last 24 hours by checking the appropriate “Yes/No” box on line 27 and, if extubated, enter the time and date in the appropriate fields.
- Record the highest and lowest measured tidal volumes in ml in the last 24 hours in the appropriate fields on line 28.
- Based on the EMR, estimate the total time in hours in the last 24 hours in which tidal volume exceeded 7 ml/kg and record in field on line 29.
- Enter the highest and lowest PEEP and Mean airway pressure in cm H2O in the last 24 hours in the appropriate fields on lines 30 and 31, respectively.
- If still intubated between 0600 and 1000 on study day 2 (or 3), record the plateau pressure and associated PEEP measured in this time interval in the indicated fields beginning on line 32. If multiple values are present, enter the value closest to 0800. If no values from that time period check the “No Values” box. If the patient was not intubated during this time period check the “Not intubated” box.

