- If arterial blood gasses are performed, enter the highest and lowest PaO2 and associated FiO2 since randomization in the appropriate fields on line 29. If only a single value enter the PaO2 and FiO2 values in the “Lowest” field and check the “Single value” box. If no arterial blood gasses were performed, check the “None” box.
- Enter total intake in ml in the field on line 34.
- Enter total output (including net volume removed by RRT) in the last 24 hours in the field on line 35.
- Indicate whether the research blood sample was collected by checking the appropriate “Yes/No” box on line 36.
- Record the date and time the research blood sample was collected and processed in the appropriate fields on line 37.
- Indicate how many 0.5 ml aliquots from the sample by checking the appropriate box on line 38.
- Record the time and date the samples were placed in the -80°C freezer in the appropriate field on line 39.
- Indicate the location of the sample in the freezer and the displayed freezer temperature at the time the samples were placed in the indicated fields on line 40.

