- Indicate whether proning protocol was initiated or stopped in the previous 24 hours on line 23.
- Beginning on line 24, record the lowest and highest values for each indicated laboratory value since randomization. If there is only one value, record it in the lowest value field, and click the “Single” box. If there are no data, check the “None” box.
- In the appropriate fields in table beginning on line 25, enter the lowest and highest blood glucose values (from finger sticks) and the date and time of the measurements for each 6-hour period since randomization. If there is only a single value, record in the “Lowest Glucose” field and check the “Single Value” box for that 6-hour time period. If there are no glucose measurements, click the “None” box for that 6-hour time period.
- If the patient was extubated prior to Study 4 skip to question 34.
- If intubated and receiving mechanical ventilation for any part of day 4 indicate all ventilator modes used in the last 24 hours by checking the appropriate boxes under line 26 and circle the mode used at 0800.
- Indicate whether the patient was extubated in the last 24 hours by checking the appropriate “Yes/No” box on line 27 and, if extubated, enter the time and date in the appropriate fields.
- Record the highest and lowest measured tidal volumes in ml in the last 24 hours in the appropriate fields on line 28.
- Based on the EMR, estimate the total time in hours in the last 24 hours in which tidal volume exceeded 7 ml/kg and record in field on line 29.
- Enter the highest and lowest PEEP and Mean airway pressure in cm H2O in the last 24 hours in the appropriate fields on lines 30 and 31, respectively.
- If still intubated between 0600 and 1000 on study day 4, record the plateau pressure and associated PEEP measured in this time interval in the indicated fields beginning on line 32. If multiple values are present, enter the value closest to 0800. If no values from that time period check the “No Values” box. If the patient was not intubated during this time period check the “Not intubated” box.
- If arterial blood gasses are performed, enter the highest and lowest PaO2 and associated FiO2 since randomization in the appropriate fields on line 33. If only a single value enter the

PaO2 and FiO2 values in the “Lowest” field and check the “Single value” box. If no arterial blood gasses were performed, check the “None” box.

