- Enter the lowest and highest values since randomization from the EMR for systolic and diastolic blood pressure and mean arterial pressure in mm Hg in the appropriate fields on line 14. Record the lowest and highest values for CVP in cm H2O. If no CVP measurements check the “CVP not available” box. If only one measurement for any of the vital signs, enter the value in the “Lowest” CVP box and check the “Single” box.
- In the table on line 15 enter for each 6-hour period in the previous 24 hours the highest and lowest recorded core temperatures, check the box next to the location of the probe, and enter the lowest recorded SpO2 value, the corresponding FiO2, and the most concurrently measured Mean Airway Pressure. If there is only a single temperature measurement during the period, record in the “Lowest” field and check the “Single value” box. If there are no SpO2 measurements during a 2-hour period, indicate by checking the “None” Box for SpO2. If the patient was receiving supplemental oxygen by NC, calculate the FiO2 using the formula:  $F_{iO_2} = 0.21 + 0.03 \times \text{flow rate in LPM}$ .
- Indicate whether the patient received corticosteroids in the last 24 hours by checking the appropriate “Yes/No” box on line 16. If “Yes,” enter the total dose in hydrocortisone equivalents using the conversion, 1 mg prednisone or methylprednisolone = 4 mg hydrocortisone and 1 mg dexamethasone = 25 mg hydrocortisone.
- Indicate whether the patient received an inhaled vasodilator in the last 24 hours by checking the appropriate “Yes/No” box on line 17. If “Yes,” indicate which agent by checking the appropriate box and the date and time the current administration was started in the indicated field.
- Indicate if the patient received vasopressor support at any time since randomization by checking the appropriate “Yes/No” box on line 18. If “Yes,” check the box next to each of the agents that was received, the highest infusion rate (and units) received, and the total hours receiving any vasopressor support. If “No” skip to question 19.
- Indicate whether proning protocol was initiated or stopped in the prior 72 hours on line 19.
- Beginning on line 20, record the lowest and highest values for each indicated laboratory value since randomization. If there is only one value, record it in the lowest value field, and click the “Single” box. If there are no data, check the “None” box.

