- If the patient was extubated prior to Study 7 skip to question 29.
- Indicate all ventilator modes used in the last 24 hours by checking the appropriate boxes under line 21 and circle the mode used at 0800.
- Indicate whether the patient was extubated in the last 24 hours by checking the appropriate “Yes/No” box on line 22 and, if extubated, enter the time and date in the appropriate fields.
- Record the highest and lowest measured tidal volumes in ml in the last 24 hours in the appropriate fields on line 23.
- Based on the EMR, estimate the total time in hours in the last 24 hours in which tidal volume exceeded 7 ml/kg and record in field on line 24.

- Enter the highest and lowest PEEP and Mean airway pressure in cm H2O in the last 24 hours in the appropriate fields on lines 25 and 26, respectively.
- If still intubated between 0600 and 1000 on study day 7, record the plateau pressure and associated PEEP measured in this time interval in the indicated fields beginning on line 27. If multiple values are present, enter the value closest to 0800. If no values from that time period check the “No Values” box. If the patient was not intubated during this time period check the “Not intubated” box.
- If arterial blood gasses are performed, enter the highest and lowest PaO2 and associated FiO2 since randomization in the appropriate fields on line 28. If only a single value enter the PaO2 and FiO2 values in the “Lowest” field and check the “Single value” box. If no arterial blood gasses were performed, check the “None” box.
- Record total intake in ml in the field on line 29.
- Record the total output (including net volume removed by RRT) in the last 24 hours in the field on line 30.
- Indicate whether the research blood sample was collected by checking the appropriate “Yes/No” box on line 31.
- Record the date and time the research blood sample was collected and processed in the appropriate fields on line 32.
- Indicate how many 0.5 ml aliquots from the sample by checking the appropriate box on line 33.
- Record the time and date the samples were placed in the -80°C freezer in the appropriate field on line 34.
- Indicate the location of the sample in the freezer and the displayed freezer temperature at the time the samples were placed in the indicated fields on line 35.

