**eTable 2: Imputed PF ratio (cells) for combinations of SpO2 (rows) and FiO2 (columns)**

	0.30	0.35	0.40	0.45	0.50	0.55	0.60	0.65	0.70	0.75	0.80	0.85	0.90	0.95	1.00
80%	148	127	111	98	89	81	74	68	63	59	55	52	49	47	44
81%	151	129	113	101	91	82	76	70	65	60	57	53	50	48	45
82%	155	132	116	103	93	84	77	71	66	62	58	55	52	49	46
83%	158	136	119	106	95	86	79	73	68	63	59	56	53	50	47
84%	162	139	122	108	97	89	81	75	70	65	61	57	54	51	49
85%	167	143	125	111	100	91	83	77	71	67	63	59	56	53	50
86%	171	147	129	114	103	94	86	79	73	69	64	61	57	54	51
87%	177	151	132	118	106	96	88	81	76	71	66	62	59	56	53
88%	182	156	137	121	109	99	91	84	78	73	68	64	61	58	55
89%	189	162	141	126	113	103	94	87	81	75	71	67	63	60	57
90%	196	168	147	130	117	107	98	90	84	78	73	69	65	62	59
91%	203	174	153	136	122	111	102	94	87	81	76	72	68	64	61
92%	213	182	159	142	128	116	106	98	91	85	80	75	71	67	64
93%	223	191	168	149	134	122	112	103	96	89	84	79	74	71	67
94%	236	202	177	157	142	129	118	109	101	94	89	83	79	75	71
95%	252	216	189	168	151	138	126	116	108	101	95	89	84	80	76
96%	273	234	205	182	164	149	136	126	117	109	102	96	91	86	82

Conditions required to use inferred P/F ratio include: (a) SpO2 values 80-96%, (b) SpO2 measured ≥10 min after FiO2 change, (c) PEEP ≥ 8 cm H2O, (d) adequate pulse oximeter wave form, and (e) qualifying inferred P/F ratio is confirmed 1-6 hrs after the initial determination.

P/F ratio criterion met within 7 ventilator days

- Yes Collect **baseline blood sample**, randomize and record randomization time and treatment assignment below
- No STOP

Is this patient currently receiving prone positioning alternating with supine positioning?

- Yes
- No

Randomization date/time:    /   /          
MONTH D D Y Y Y Y TIME (0-2400)

Treatment assignment (check one)

- Therapeutic Hypothermia
- Usual Treatment

Initiate sedation, NMB, and cooling protocol for subjects randomized to Therapeutic Hypothermia

Complete Baseline information CRF.

See schedule for first week blood and data collection below.

--	--

[figure not shown]
SITE ID

--	--	--	--

PATIENT ID

--	--	--

LETTER CODE

- Collect baseline blood and complete Baseline CRF based on 24h preceding randomization
- Collect day 1 blood and complete Day 1 CRF at 0800 on randomization day + 1; (the duration of day 1 may be 8h 1 min to 31h 59 min as indicated by the examples a - c)

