- Collect blood and complete CRFs for Day 2, 3, 4, and 7 at 0800 on randomization day + 2, +3, +4, and +7 covering the prior 24h period

SITE ID		PATIENT ID				LETTER CODE			

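### Labs and blood gases on the Day 2, 3, 4 and 7 forms: the item instructions ask for extremes since randomization, the schedule for the prior 24 hours

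*Protocol*

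**What the plan says.** **Item instructions.** Section 10.5 (Days 2 and 3) asks staff to "record the lowest and highest values for each indicated laboratory value since randomization", and sections 10.6 (Day 4) and 10.7 (Day 7) repeat it. The highest and lowest PaO2, each with its FiO2, are to be entered "since randomization in the appropriate fields on line 29" in 10.5, "since randomization in the appropriate fields on line 33" in 10.6 and "since randomization in the appropriate fields on line 28" in 10.7. Blood pressure follows the same rule: "Enter the lowest and highest values since randomization from the EMR for systolic and diastolic blood pressure and mean arterial pressure" (10.5, repeated in 10.6 and 10.7). So do vasopressors: "Indicate if the patient received vasopressor support at any time since randomization" (10.7, with the same wording in 10.5 and 10.6).

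**Schedule.** The first-week schedule closes the Screening/Enrollment/Randomization Source Document in the Appendix. It has the Day 2, 3, 4 and 7 forms completed at 0800, "covering the prior 24h period". For Day 1 it notes that "the duration of day 1 may be 8h 1 min to 31h 59 min".

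**Forms.** On the supplied Day 03, 04 and 07 forms, the laboratory blocks (lines 24, 24 and 20) and the blood-gas blocks (lines 33, 33 and 28) print no time window. The blood pressure and vasopressor blocks on the same forms do print a 24-hour window. The Day 02 form is not in the supplied text, so nothing is claimed about it.

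**Analysis.** The SAP fits a repeated-measures mixed model to physiological and biomarker secondary outcomes over days 0, 1, 2, 3, 4 and 7.

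**The concern.** Two rules govern the same field. Under the item instruction the value is a running extreme. From Day 1 on, the lowest platelet count can only fall or stay level, the highest creatinine can only rise or stay level, and the lowest PaO2 cannot rise. The ratio formed from that PaO2 can improve only if a new, lower PaO2 happens to come with a lower FiO2. A Day 4 or Day 7 entry then does not describe Day 4 or Day 7. If some staff follow the instruction and others the schedule, one field holds different windows in different patients, and nothing in the field shows which.

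Four of the SAP's six analysis days carry this wording. SOFA is a secondary outcome (section 1.1) and part of the third aim (section 1.2). If its laboratory and oxygenation components are taken from these fields over time, recovery would be masked and an early transient abnormality carried forward.

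**Working it through.** The plan gives no figure to reproduce. The check compares window lengths and then asks which outcomes use the fields.

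**Window length.** Inputs: Day 1 lasts 8 h 1 min to 31 h 59 min, and each later study day adds 24 h (both from the schedule). The window since randomization on study day d is the Day 1 length + 24 × (d − 1) hours. For Day 4 this is 8 h 1 min + 72 h = 80 h 1 min, up to 31 h 59 min + 72 h = 103 h 59 min.

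| Form | Since randomization | Multiple of 24 h | 24 h as share of it |
|---|---|---|---|
| Day 2 | 32 h 1 min to 55 h 59 min | 1.33–2.33 | 43–75% |
| Day 3 | 56 h 1 min to 79 h 59 min | 2.33–3.33 | 30–43% |
| Day 4 | 80 h 1 min to 103 h 59 min | 3.33–4.33 | 23–30% |
| Day 7 | 152 h 1 min to 175 h 59 min | 6.33–7.33 | 14–16% |

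**Number of panels.** Section 6 schedules the basic metabolic panel and CBC twice a day on Days 0–4, one per 12 h. Window ÷ 12 h gives 2.7–4.7 panels on Day 2, 4.7–6.7 on Day 3 and 6.7–8.7 on Day 4, against 2 in 24 h. This covers those two panels only. Section 6 sets no frequency for bilirubin or transaminases, and blood gases are taken when available.

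**Forms exposed.** 20 patients × 4 forms = 80 at most, if every patient is alive with all forms completed.

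**Illustration, on assumptions not in the documents.** Take a patient with no true change, values with SD 1, two draws a day on Days 1–4 and one a day on Days 5–7, and a correlation of 0, 0.5 or 0.8 between consecutive draws. In a simulation of 200,000 such patients, the mean recorded low since randomization moves from Day 1 to Day 7 as follows:
- correlation 0: −0.57 to −1.59, a fall of 1.02 SD
- correlation 0.5: −0.40 to −1.42, a fall of 1.02 SD
- correlation 0.8: −0.25 to −1.08, a fall of 0.83 SD

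With a 24 h window the low stays level over Days 1–4. This is drift within a patient, not a difference between arms.

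**Which outcomes use the fields.** Section 1.1 lists OSI, driving pressure, SOFA and biomarkers among the secondary outcomes. OSI comes from the SpO2, FiO2 and mean airway pressure table, driving pressure from the 0600–1000 plateau pressure, and biomarkers from research samples. None of these uses the affected fields. The primary outcomes are temperature control and safety measures, also outside them. That leaves SOFA. Section 3.3 documents it at randomization, the section 6 table has no SOFA row, the SAP gives no derivation, and the supplied forms have no Glasgow Coma field.

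**The case against.** The strongest reply is that the packet already points to 24 hours. The schedule is printed inside it, and the daily pages are headed as daily data. On the Day 03 and 04 forms, the items directly above and below the laboratory block (proning and finger-stick glucose) both refer to 24 hours. That helps, and it would be wrong to say that nothing near the point of entry suggests the shorter window. It does not settle the matter. On the Day 07 form the line just above the laboratory block asks about 72 hours. On all three forms the line after the blood-gas block (total intake) is cumulative. The heading about treatments received in the last 24 hours covers treatments, and the 0600–1000 heading belongs to plateau pressure.

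For blood pressure and vasopressors the reply largely succeeds. The instruction conflicts in the same way, but the form's own question states 24 hours, so an error requires ignoring what is printed.

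A reader might infer that the phrase was copied from the Day 1 instructions by oversight. The documents do not establish that. Section 10.5 does send blood pressure to line 15 and blood gases to line 29, where the Day 03 form has lines 18 and 33. But 15 and 29 do not match Day 1 either (lines 19 and 34), and sections 10.6 and 10.7 give correct line numbers with the same phrase.

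It can also be said that the same wording applies to both arms and that the 24-hour values are probably recoverable from the electronic record and retained source documents. Both are fair. They limit the harm, but recovery would cost re-abstraction.

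**Conclusion.** The contradiction is certain for laboratory values and blood gases: the item instructions and the schedule cannot both be followed on Days 2, 3, 4 and 7, and the entry blocks do not choose between them. The instructed window is 1.33–2.33 times the scheduled one on Day 2, rising to 6.33–7.33 times on Day 7. The matching conflict for blood pressure and vasopressors carries little risk.

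A reader might go further and infer that the SOFA analysis, or the comparison between arms, is biased. The documents do not support that. It is an inference that SOFA is analysed over time and built from these fields, and without a Glasgow Coma field the supplied forms alone could not give a full score. Neither the size nor the direction of any bias between arms can be derived. This is an inexpensive defect in data definition that should be fixed, not a threat to the primary results.

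**What to change.** - In sections 10.5–10.7, replace the cumulative wording with the last 24 hours, 0800 to 0800, for labs, blood gases, blood pressure and vasopressors. Print that window above the laboratory and blood-gas blocks on the Day 2, 3, 4 and 7 forms.
- For finger-stick glucose in 10.5 and 10.6, refer to the four printed six-hour rows. They run from 0601 to 0600, so an 0800 window would create a new mismatch.
- If SOFA is analysed over time, add an SAP sentence saying that its Day 2, 3, 4 and 7 components use these 24-hour fields.

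**Cost.** Wording in the manual and forms and one SAP sentence; no new visits or measurements. The downside is that, with no Day 5 or Day 6 form in the Appendix list, laboratory and blood-gas extremes on those days would not be captured. If they are wanted, add a separately labelled days 5–7 field.

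**Reconcile separately.** Fluid output and stopping of renal replacement therapy are 24-hour items in 10.5–10.7 but cumulative on the forms. The Day 7 SpO2, FiO2 and mean airway pressure table, which feeds OSI, covers 24 hours in 10.7 (four six-hour rows) but 72 hours on the form (3 + 4 + 4 + 1 = 12 rows). Its dated rows already contain the last 24 hours, which limits the harm.
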